7.5 Interim Analyses and Data Monitoring (as applicable)

No Interim Analysis is planned.

7.6 Multiple Testing

The primary efficacy endpoints (Mean change from baseline in tear osmolarity in the study eye at Day 84 and Mean change from Screening in OSDI score Day 84) comprise a set of hypotheses that will be tested in a hierarchical fashion using Hochberg's procedure. The Hochberg procedure is a step-up procedure. The procedure starts with the largest p-value, which is compared to the largest endpoint-specific critical value ($\alpha=0.05$). If the largest p-value is less 0.05, then the method concludes that there are significant treatment effects for all endpoints.

The differences between the 2 treatment groups for these endpoints will be tested with a significance level of 0.05. In order to control the Type I error rate these 2 endpoints will be tested sequentially in the method described above. For instance, if significance level for the null hypothesis for the tear osmolarity endpoint is the largest and is less than 0.05, OSDI endpoint will also declared significant at $P \leq 0.05$.

8 Summary of Study Data

All continuous variables will be summarized using the following descriptive statistics: n (non-missing sample size), mean, SD, median, maximum and minimum. The frequency and percentages (based on the non-missing sample size) of observed levels will be reported for all categorical measures. In general, all data will be listed, sorted by center, treatment and subject, and when appropriate by visit number within subject. All summary tables will be structured with a column for each treatment in the order (Placebo, OmegaD) and will be annotated with the total population size relevant to that table/treatment, including any missing observations.

8.1 Subject Disposition

A CONSORT diagram will be included delineating subjects screened, randomized and followed will be included.

8.2 Derived variables

Changes from Baseline are the derived variables.

8.3 Protocol Deviations

From [Section 7.2](#) in the protocol the following are deviations that may be associated with subject withdrawal during the post randomization period as they may affect efficacy assessments.

- Use of Lid scrubs with over-the-counter products and/or warm compresses.
- Chronic daily use of systemic narcotics for any chronic pain syndrome
- LASIK or photorefractive keratectomy
- Ophthalmic artificial tear drop use within 2 hours prior to any study visit.
- Contact lens wear within 12 hours of any study visit.
- Cauterization of the punctum or existing silicone punctal plug(s); silicone plug removal or collagen plug insertion or removal
- Started or changed the dose of systemic medications known to affect tear production
- Any chronic use of systemic antihistamines
- Use of any topical prescription ophthalmic medications, topical macrolides, or oral nutraceuticals (fish, flax, black currant seed oils, etc.)
- Use of oral tetracyclines or oral macrolides; use of isotretinoin.
- Chronic daily use (defined as > 7 consecutive days at the recommended dosing frequency) of oral NSAIDs
- Becoming Pregnant.
- Participation in any other drug or device clinical investigation.
- Lack of compliance with respect to timing of dosing of vitamins relative to investigational product.

Subjects with these deviations will be examined and data may be excluded from the per-protocol analysis.

8.4 Demographic and Baseline Variables

Demographic variables include age, gender and clinical site.

8.5 Concurrent Illnesses and Medical Conditions

Medical History and Ocular History are coded with MedDRA V22.1. Concomitant Medications are coded with WHO Drug v. September 2019.

8.6 Treatment Compliance

Compliance will be assessed as the percent of Soft-Gels returned versus dispensed. For those subjects delaying clinic visits due to COVID-19, additional IP was provided as needed.

9 Efficacy Analyses

All efficacy variables will be listed by subject within study center. Data will be summarized by treatment group. N, Mean, Median, SD, Minimum and Maximum will summarize continuous efficacy

variables, whereas number and percent will summarize categorical efficacy variables.

As per E9 Statistical Principles for Clinical Trials, the main treatment effect will be estimated using Model (1) that allows for center differences but does not include a term for treatment-by-center interaction. In the presence of a significant treatment effect, heterogeneity of the treatment effect will be explored by adding treatment by center interaction terms (Model (2)). If no statistically significant interaction is seen, then the estimated treatment effect from Model (1) will be provided. If an interaction between treatment and center is present the nature of the interactions will be explored (quantitative or qualitative) and reported.

Model (1): $y_{ijk} = \mu + c_i + t_j + \xi_{ijk}$, where:

c_i is fixed effect of the i th center

t_j is the fixed effect of the j th treatment

y_{ijk} is the response of the k th subject in j th treatment group within the i th center

ξ_{ijk} is the random measurement error in observing y_{ijk}

μ is a constant effect common to all responses

$i=1, \dots, c$, $j=1$ or 2 and $k=1, \dots, n_{ij}$.

Model (2): $y_{ijk} = \mu + c_i + t_j + (ct)_{ij} + \xi_{ijk}$ where $(ct)_{ij}$ is the fixed interaction effect between the i th center and j th treatment.

Analyses will be using the SAS system.

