- Mean change from Screening in Schirmer's test (anesthetized) score in the study eye at Visit 4 (Day 84)

Exploratory Efficacy Endpoint:

- Proportion of subjects with meibomian gland dysfunction grade of 0 on both meibomian orifice size and telangiectasia scales in the study eye at Visit 4 (Day 84)

Safety Endpoint:

- Incidence of AEs

Statistical Methods:

Analysis Populations:

- Intent-to-treat (ITT): The ITT population will include all randomized subjects.
- Per protocol (PP): The PP population will include all ITT subjects who remain in the study through Visit 4 and who did not deviate from the protocol in any way likely to seriously affect the primary outcome of the study.
- Safety: The safety population will include all subjects who have received at least one dose of the IP.

Efficacy analysis will be conducted on the ITT population and on the PP population. Safety analyses will be performed using the safety analysis population.

Statistical Analyses:

Analysis of TBUT, meibomian gland dysfunction, tear osmolarity, and Schirmer's test scores (anesthetized) will utilize the designated study eye (worse eye at Baseline as defined by higher tear osmolarity score; if both eyes score equally on tear osmolarity, the eye with the lower TBUT score will be chosen, and if still equal, the right eye will be the study eye) to assess the significance of the differences between OmegaD and placebo. The unit of analysis for OSDI symptoms will be the subject.

Statistical significance for the comparison of means will utilize an analysis of covariance using treatment, center, and baseline values as covariates. Statistical significance for binary data will be assessed by a chi-square, Fisher's exact, or Cochran-Mantel-Haenszel test.

Descriptive statistics will be used to summarize continuous outcomes (number of subjects, mean, standard deviation (SD) or standard error of the mean, median, maximum, and minimum) and categorical variables (frequency and percentage) at each assessment time point. All summary tables will be supported with individual subject data listings.

A comprehensive Statistical Analysis Plan will be completed prior to completion of data collection.

Sample Size:

A total of 150 subjects per groups is planned. Power considerations for each endpoint are described below.

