7.3 Covariates and Subgroups

The primary analysis will use a statistical model that adjusts for trial center as well as the pre-randomization value of the efficacy variable. The effects of center will be examined and potential interactions between centers and IP.

15 Centers with 20 subjects per center are planned. In the event of underperformance (<6 per center) in recruitment among a number of centers, the underperforming centers will be pooled. The strategy for pooling will consider location of the center (academic or clinic) and geography. The pooling will be decided prior to unmasking of the data.

There are no *a priori* subgroups considered for inclusion in the statistical analyses. However, treatment outcomes by gender and age will be displayed.

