7.4 Missing Data

The protocol requires that, for subject discontinuation before Visit 4 (Day 84), every effort should be made to keep the subject in the study and conduct all study visits as scheduled or, failing that, to perform all Visit 4 (Day 84) procedures at the visit the subject is discontinued. Also, due to COVID-19, subjects nearing the Day 84 assessment, but not allowed to attend clinic, were allowed to continue IP until a final visit could occur. The visit times may be well over the times in the nominal visit window but data from these visits will be included provided that the subject continued to dose IP and was dosing IP for at least 7 days prior to their V4 visit. For these subjects those data will not be considered missing and used in the primary analyses for the Full Analysis Population.

Efficacy data (osmolarity and/or OSDI) for subjects receiving IP may be missing for Day 84 (e.g. failure to return, Adverse Event). *A priori* assumptions are that these will be few. The missing data handling method for the primary endpoints, based on the population of randomized and treated subjects, will be as follows: Regression and propensity scores methods of multiple imputation will be used for missing OSDI and tear osmolarity scores at Visit 4 (week 12). As data will only be missing at visit 4, monotone missingness will be assumed. OSDI and Total Osmolarity will be assessed separately.

The PROC MI procedure in SAS will be used. In addition to the regression method, propensity scores will also be employed. The output of interest from PROC MI is a data set containing multiple repetitions of the original data set, along with the newly imputed values. Each of these output datasets will be analyzed using the statistical model that adjusts for trial center as well as the pre-randomization value of the efficacy variable. The MIANALYZE procedure in SAS will be used to combine the results from output datasets from PROC MI.

The model structure in SAS for the OSDI endpoint will be as follows for the regression and propensity scores (similar models for Total Osmolarity will be generated):

```
DATA OSDI_CH; set omegad.osdi_CH; keep trt subject center osdi_v1  
osdi_v4 trt;  
proc mi data=osdi_CH seed=501213 nimpute=5 out=OSDI_outreg;  
class center trt;  
monotone reg (OSDI_v4=osdi_v1 center trt);  
var center trt OSDI_v1 OSDI_v4;  
run;  
proc mi data=osdi_CH seed=501213 nimpute=5 out=OSDI_outprop;  
class center trt;  

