9.1 Primary Efficacy Analysis

The null and alternative hypotheses for this model are $H_0: \alpha=0$ versus $\alpha \neq 0$. Treatment will be tested at the 2-sided 5% significance level. A test for interaction will be performed if the overall effect for investigational product in the model for main effects is significant. In the event of a lack of interaction between center and investigational product the results from the main effect model will be reported (IP and Center). If a beneficial treatment effect is observed for both primary variables (OSDI/tear osmolarity) then OmegaD would be declared effective in dry eye disease.

Box plots will be used to check for normality prior to analysis. Transformations may be used to allow for conformance to normality. Data from previously reported clinical trials in dry eye disease, examining changes in both OSDI and tear osmolarity, were used in estimating sample sizes. Methods sections and results from publications examining these outcomes reflect use of data without need for transformations to achieve normality. However, in the event that normality is not observed, the van Elteren test will be employed in the event of nonnormal distributions. The van Elteren test is an extension of the Wilcoxon rank sum test for detecting differences in the distributions of the response of interest between groups in a stratified experiment.

Statistical tests will be two-sided. Methods for handling missing data are described in [Section 8.4](#).

All assumptions for regression models will be assessed by viewing plots of the residual values.

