9.2 Secondary Efficacy Analyses

Slit lamp examinations, TBUT and Schirmer's test will be analyzed as secondary endpoints using the model above on both the per-protocol and intention-to-treat populations. Results from the secondary endpoints will be reported. No formal inferences are planned for secondary endpoints.

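### The primary model written in SAP Section 9 leaves out the baseline covariate that the protocol and two other SAP sections call for

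*SAP*

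**What the plan says.** **Without baseline.** SAP Section 9 states that "the main treatment effect will be estimated using Model (1) that allows for center differences but does not include a term for treatment-by-center interaction". Model (1) is y = constant + center + treatment + error. Each symbol is defined there, and none is a baseline value. Model (2) adds only the center-by-treatment interaction. SAP 9.1 builds the primary hypothesis test on this model and says that, absent an interaction, "the results from the main effect model will be reported (IP and Center"). SAP 8.2 adds that "Changes from Baseline are the derived variables", so the response in Model (1) reads as change from baseline.

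**With baseline.** SAP 7.3: "The primary analysis will use a statistical model that adjusts for trial center as well as the pre-randomization value of the efficacy variable". SAP 7.4 says each imputed data set will be "analyzed using the statistical model that adjusts for trial center as well as the pre-randomization value of the efficacy variable". The protocol synopsis and protocol 11.6 both specify an "analysis of covariance using treatment, center, and baseline values as covariates".

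**Which governs.** No sentence settles this. SAP Section 15 reports no protocol change with a material effect on the statistical methods, so Model (1) is not a declared departure from the ANCOVA.

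**The concern.** The SAP supports two different primary analyses. Taken literally, imputed data sets are analyzed with baseline adjustment under 7.4, while the model of Section 9 is unadjusted.

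Using change as the response does not supply the missing covariate. Model (1) on change fixes the slope of the Day 84 value on baseline at 1; ANCOVA estimates it. A slope below 1 is plausible here: both baselines are noisy readings that also served as entry criteria, and the study eye is the one with the higher osmolarity at that same Baseline visit.

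Three things are at stake:

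- The unadjusted estimate is less precise.
- It is not corrected for chance baseline imbalance.
- The covariate could be chosen after unmasking.

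The loss of power matters more because the SAP's only stated rule for declaring efficacy is "If a beneficial treatment effect is observed for both primary variables (OSDI/tear osmolarity) then OmegaD would be declared effective in dry eye disease".

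**Working it through.** **Inputs from the documents** (protocol 11.3, SAP Section 6): 150 per group; two-sided alpha 0.05; tear osmolarity difference 8 mOsm/L with SD of change 19; OSDI difference 7 points with SD of change 17.

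**Step 1. The plan's own power.** Standard error = SD × √(2/150) = SD × 0.1155.

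- Osmolarity: 19 × 0.1155 = 2.19; noncentrality 8/2.19 = 3.65; power 95.3% (noncentral t).
- OSDI: 17 × 0.1155 = 1.96; noncentrality 7/1.96 = 3.57; power 94.5%.

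Both agree with the stated figure of about 95%. That calculation uses an unadjusted t-test on change, so Model (1) does not undermine the planned N.

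**Step 2. Assumptions for the adjusted model.** The documents give neither the baseline SD (sb) nor the slope of Day 84 on baseline (b). Assumed: b = 0.2, 0.4, 0.6; sb = 8 or 12 (osmolarity) and 14 or 18 (OSDI). The SD of change stays at 19 or 17. The OSDI case b = 0.2, sb = 18 is left out because it implies a Day 84 SD of only 9.7 and a baseline–change correlation of −0.85.

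**Step 3. Residual variance.** Since Var(change) = (1−b)²·sb² + residual variance, the ratio to Model (1) is [Var(change) − (1−b)²·sb²] / Var(change).

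- Osmolarity, b = 0.2, sb = 12: (361 − 0.64 × 144)/361 = 268.84/361 = 0.745.
- Osmolarity, b = 0.6, sb = 8: (361 − 0.16 × 64)/361 = 350.76/361 = 0.972.
- OSDI, b = 0.2, sb = 14: (289 − 0.64 × 196)/289 = 163.56/289 = 0.566.
- OSDI, b = 0.6, sb = 14: (289 − 0.16 × 196)/289 = 257.64/289 = 0.891.

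**Step 4. Precision and power at the planned effects.** The residual SD replaces the SD of change in Step 1. The imbalance row is (1−b) × 2·sb × 0.1155, the shift in the unadjusted estimate from a chance baseline difference of 2 standard errors.

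| | Osmolarity, no baseline | Osmolarity, with baseline | OSDI, no baseline | OSDI, with baseline |
|---|---|---|---|---|
| 95% CI half-width | 4.32 | 3.73–4.26 | 3.86 | 2.91–3.65 |
| Power | 95.3% | 95.8–98.8% | 94.5% | 96.4–99.7% |
| Shift from 2-SE imbalance | 0.7–2.2 mOsm/L | adjusted for | 1.3–2.6 points | adjusted for |

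**Step 5. Power for both primaries together**, treating the endpoints as independent.

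- Planned effects: 0.953 × 0.945 = 0.90 without baseline; from 0.958 × 0.964 = 0.92 to 0.988 × 0.997 = 0.985 with it.
- Half the planned effects (4 mOsm/L and 3.5 points): 0.443 × 0.428 = 0.19 without; from 0.454 × 0.469 = 0.21 to 0.558 × 0.656 = 0.37 with.
- At a between-endpoint correlation of 0.5, the planned-effect figures are 91% without and 93–99% with.

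**Step 6. How often the two models disagree at P ≤ 0.05.** Simulation of 40,000 trials per setting, 15 centers with 10 subjects per arm each, normal errors.

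| | Osmolarity | OSDI |
|---|---|---|
| Disagreement, planned effect | 1.4–3.9% | 3.0–5.4% |
| Disagreement, half effect | 5–19% | 11–29% |
| Of those at half effect, only ANCOVA significant | 61–80% | 69–89% |
| Type I error if the better model is picked after unmasking | 5.7–7.4% | 6.7–8.0% |

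Under no effect, each model alone rejected in 4.9–5.2% of trials.

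**Step 7. A different assumption.** With equal variances at baseline and Day 84 and correlation r between them, residual SD = SD of change × √((1+r)/2). For r = 0.3 to 0.7 the power is 99.5% down to 97.7% (osmolarity) and 99.3% down to 97.2% (OSDI). The direction is the same; the size depends on the assumption.

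**The case against.** The best reply is that the plan already contains the adjustment. SAP 7.3, the section on covariates, states it for the primary analysis; SAP 7.4 and both protocol passages agree, and no sentence drops it. Section 9 introduces Model (1) to settle whether an interaction term is included, so the equation may be schematic and the two named terms in 9.1 shorthand. Validity and sizing are untouched, the gain is over and above the power the trial was sized for, and its size rests on assumed values.

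Much of this stands. The weight of the text favors the adjusted model, each model alone holds 5%, and the stated power is met. The largest osmolarity figures come from one setting (slope 0.2, baseline SD 12), and the documents do not plan for half the effect. The 5.7–8.0% error rates apply only if someone fits both models after unmasking and keeps the better one; they are not the trial's error rate. The rule in SAP 9.1 is worded as a sufficient condition, and the testing schemes in SAP 7.6 and protocol 11.6.1 can each support a claim on one endpoint, so the joint-power figures apply when both are needed.

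None of this removes the conflict. The equation is complete, its terms are all defined, and the hypothesis test in 9.1 refers to it. Half-size effects are also a fair case to examine: protocol 4.2 reports that the sponsor's earlier trial found no OSDI difference (P = 0.52) and attributed this to an unexpectedly high placebo response.

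**Conclusion.** The concern holds and should be fixed before unmasking. Neither written model is the ANCOVA that the protocol and SAP 7.3 and 7.4 describe, and no text resolves the difference. The main harm is lost precision: under the assumed slopes and baseline SDs, baseline adjustment removes about 3–26% of the residual variance for tear osmolarity and 11–43% for OSDI. A smaller harm is that the covariate is left open to choice. If the slope were near 1, so that baseline was unrelated to change, the variance ratio would approach 1.00 and the two models would nearly coincide. For TBUT and Schirmer's test the point is consistency only, since SAP 9.2 says "No formal inferences are planned for secondary endpoints".

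**What to change.** Before unmasking:

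- Write Model (1) as constant + center + treatment + slope × baseline + error, and Model (2) as the same plus center-by-treatment.
- Define baseline as the Day 1 study-eye value for tear osmolarity and the Screening score for OSDI.
- In SAP 9.1, name the reported model's terms as IP, center and baseline value. State the null hypothesis on the treatment term; the symbol α used there appears in neither model.
- Say that this one model applies to both observed and imputed data.
- For consistency, use it with Screening values for TBUT and Schirmer's test.

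The cost is one model term and a few lines of SAP wording. Every covariate is already collected and N does not change. This settles the covariate only; the optional transformation, the van Elteren fallback and the choice between the two imputation methods are separate matters.

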9.1 Primary Efficacy Analysis

The null and alternative hypotheses for this model are $H_0: \alpha=0$ versus $\alpha \neq 0$. Treatment will be tested at the 2-sided 5% significance level. A test for interaction will be performed if the overall effect for investigational product in the model for main effects is significant. In the event of a lack of interaction between center and investigational product the results from the main effect model will be reported (IP and Center). If a beneficial treatment effect is observed for both primary variables (OSDI/tear osmolarity) then OmegaD would be declared effective in dry eye disease.

Box plots will be used to check for normality prior to analysis. Transformations may be used to allow for conformance to normality. Data from previously reported clinical trials in dry eye disease, examining changes in both OSDI and tear osmolarity, were used in estimating sample sizes. Methods sections and results from publications examining these outcomes reflect use of data without need for transformations to achieve normality. However, in the event that normality is not observed, the van Elteren test will be employed in the event of nonnormal distributions. The van Elteren test is an extension of the Wilcoxon rank sum test for detecting differences in the distributions of the response of interest between groups in a stratified experiment.

Statistical tests will be two-sided. Methods for handling missing data are described in [Section 8.4](#).

All assumptions for regression models will be assessed by viewing plots of the residual values.

9.2 Secondary Efficacy Analyses

Slit lamp examinations, TBUT and Schirmer's test will be analyzed as secondary endpoints using the model above on both the per-protocol and intention-to-treat populations. Results from the secondary endpoints will be reported. No formal inferences are planned for secondary endpoints.

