The site will collect unused IP and the daily IP diary, update concomitant medications, perform a urine pregnancy test (women of childbearing potential only), conduct final ophthalmic examinations (OSDI questionnaire [overseeing subject completion], tear osmolarity, meibomian gland dysfunction grading, slit lamp examination, TBUT, and Schirmer's test [anesthetized]), HS-Omega-3 Index Test via fingerstick blood sample, assess AEs, record subject's answer to yes/no question, "During the study, did you regularly take any vitamins within 2 hours of taking your study medication?", and conduct final IP accountability and diary review.

Clinical site personnel will document all received and returned IP at each visit and review the IP diary. IP accountability will be conducted by the monitor at each applicable monitoring visit.

If a subject is discontinued from IP before Visit 4 or is generally noncompliant with the protocol, every effort should be made to keep the subject in the study and conduct all study visits as scheduled or, failing that, to perform all Visit 4 procedures at the visit the subject is discontinued.

Subjects who have already completed their Day 84 Final Study Visit at the time of this Protocol Amendment (V4.0) will be contacted by the site to establish their compliance with dosing of any vitamins (to be taken more than 2 hours before or after study medication) during the study.

Efficacy Assessments:

Signs: Tear osmolarity, meibomian gland dysfunction grading, TBUT, Schirmer's test (anesthetized)

Symptoms: OSDI questionnaire

Pharmacokinetics: HS-Omega-3 Index Test

Safety Assessments:

Safety assessments will include slit lamp examination and collection of AEs.

Criteria for Evaluation:

Primary Efficacy Endpoints:

The primary efficacy endpoints comprise a set of hypotheses that will be tested in a hierarchical fashion.

- Mean change from baseline in tear osmolarity in the study eye at Visit 4 (Day 84)
- Mean change from Screening in OSDI score at Visit 4 (Day 84)

The differences between the 2 treatment groups will be tested with a significance level of 0.05. In order to control the Type I error rate these 2 endpoints will be tested sequentially in the order described above. If the null hypothesis for the tear osmolarity endpoint can be rejected at $P \leq 0.05$, OSDI endpoint will be tested at $P \leq 0.05$.

Secondary Efficacy Endpoints:

- Mean change from baseline in TBUT in the study eye at Visit 4 (Day 84)

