9.3. Safety Assessments

9.3.1. Slit Lamp Examination

A routine slit lamp examination will be performed to evaluate the anterior segment of the eye, including lids, cornea, conjunctiva, anterior chamber, iris, and lens. Abnormalities will be documented.

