11.4.2. Safety Analysis Population

The safety population will include all subjects who have received at least one dose of the IP. All safety analyses will utilize the safety population.

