11.7. Safety Analyses

Safety data will be presented in tables of descriptive statistics and frequency distribution. All summary tables will be supported with individual subject data listings.

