10.7 Other Safety Measures

N/A

11 Pharmacokinetics (N/A)

N/A

12 Other Analyses

N/A

13 Reporting Conventions

P-values ≥ 0.001 will be reported to 3 decimal places; p-values less than 0.001 will be reported as " <0.001 ". The mean, SD, and any other statistics other than quantiles, will be reported to one decimal place greater than the original data. Quantiles, such as median, or minimum and maximum will use the same number of decimal places as the original data. Estimated parameters, not on the same scale as raw observations (e.g. regression coefficients) will be reported to 3 significant figures.

14 Quality Assurance of Statistical Programming (As Applicable)

The SAS system will be used to create analysis data sets, statistical analyses and summary tables and listings.

Any population to be used in a table, analysis or graphical display will be explicitly set at the start of a block of code that computes the output.

Any outputs will have the

- date and time included
- the name of the code file that produced the analysis
- the author

At the start of any code file there will be a set of comments that give

- the author
- the date and time of writing
- references to inputs and outputs
- reference to any parent code file that runs the child code file

15 Summary of Changes to the Protocol and/or SAP

As of this date no changes to the protocol have been made that materially affect the statistical methods section in the protocol.

16 References

¹Restasis® (cyclosporine ophthalmic emulsion, 0.05%) US Prescribing Information.

²XiIDRA® (lifitegrast ophthalmic solution), US Prescribing Information, Initial U.S. Approval: 2016

³Study of the Safety and Efficacy of OmegaD Softgels in the Treatment of Dry Eye Disease: ClinicalTrials.gov Identifier: NCT02980224

⁴Smith, data on file.

⁵Sullivan BD et al, An objective approach to dry eye disease severity. Invest Ophthalmol Vis Sci. 2010 Dec; 51(12):6125-30.

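### SAP 9.2 analyses slit lamp examination as a secondary efficacy endpoint with a linear model, although the protocol makes it a safety assessment with unscored findings, and SAP section 10 gives it no safety summary

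*SAP*

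**What the plan says.** **Protocol.** The synopsis states: "Safety assessments will include slit lamp examination and collection of AEs". Its list of efficacy signs is separate and leaves slit lamp out: "Signs: Tear osmolarity, meibomian gland dysfunction grading, TBUT, Schirmer's test (anesthetized"). Section 9.3.1, under Safety Assessments, describes the procedure: "A routine slit lamp examination will be performed to evaluate the anterior segment of the eye, including lids, cornea, conjunctiva, anterior chamber, iris, and lens". On recording it says only: "Abnormalities will be documented". No grade or score is defined. Section 11.7 sets the form of reporting: "Safety data will be presented in tables of descriptive statistics and frequency distribution". Section 11.4.2 sets the population: "All safety analyses will utilize the safety population". Section 11.6.2 gives TBUT and Schirmer's test as the secondary efficacy endpoints.

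**SAP.** Section 9.2 puts slit lamp examinations beside TBUT and Schirmer's test and says that they "will be analyzed as secondary endpoints using the model above on both the per-protocol and intention-to-treat populations". The same section plans no formal inference for secondary endpoints. Sections 4.2 and 5.3 list TBUT and Schirmer's test as the secondary endpoints and do not list slit lamp. Section 10 covers adverse events, exposure, deaths and SAEs, pregnancies, and medications. The entry under "10.7 Other Safety Measures" is N/A.

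**The concern.** Safety is part of the primary objective in both documents, and slit lamp is one of only two safety assessments that the protocol names. It is also the only eye examination scheduled at Day 42. If the SAP is programmed as written, the findings are sent to an efficacy section under a model that needs a numeric response, and the safety section has no entry for them. A reader of the clinical study report who looks for ocular findings under safety would find only those that were reported as adverse events. The efficacy section would hold an analysis whose response variable is nowhere defined.

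**Working it through.** No figure in the plan depends on this point, so there is nothing to reproduce. The check sets the sections side by side.

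1. **Classification.** Protocol synopsis and 9.3.1: safety. Protocol list of efficacy signs and 11.6.2: not included. SAP 4.2 and 5.3: not a secondary endpoint. SAP 9.2: secondary endpoint. SAP 9.2 stands alone against every other place. SAP section 15 reports no protocol change that materially affects the statistical methods, and it does not explain the move.

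2. **Could SAP 9.2 mean the meibomian gland grading, which is also done at the slit lamp?** No. The protocol's schedule of procedures gives that grading its own row, and SAP 9.3 handles it as the exploratory endpoint.

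3. **Fit of the model.** The model in SAP section 9 has one numeric response per subject, fixed effects for center and treatment, and an additive error. The slit lamp data are abnormalities noted in six structures (lids, cornea, conjunctiva, anterior chamber, iris, lens) of two eyes, with no score. The SAP defines no slit lamp variable, no rule for combining structures and no choice of eye. SAP 8.2 names changes from baseline as the derived variables, and such a change has no meaning for an unscored finding. Two programmers could not be expected to produce the same analysis.

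4. **Population.** SAP 9.2 uses the PP and ITT sets, and the protocol asks for the safety set. SAP 7.2.1 defines the full analysis (ITT) set as randomized subjects who received any product. SAP 7.2.3 defines the safety set as subjects who received at least one dose. Membership is practically the same, so the ITT analysis loses almost nobody whom the safety set would include.

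5. **What still reaches a table.** SAP section 8 commits to frequencies and percentages for all categorical measures, with a column per treatment. SAP section 9 repeats this for categorical efficacy variables. Under Protocol 9.6.1.1, an abnormal result counts as an adverse event if it causes signs or symptoms, is clinically significant or requires therapy. Such findings enter the AE tables of SAP section 10. What remains without a safety summary is the set of findings below that threshold.

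6. **Extent.** Slit lamp is done at four visits, but Screening and Baseline precede dosing, so two visits are on treatment. With the SAP's recruitment target of 320, the upper bound is 320 × 2 = 640 on-treatment examinations, each of both eyes. The actual number will be lower, because the COVID-19 phone visits cannot supply a slit lamp examination and some subjects will withdraw. The documents give no rate of findings below the AE threshold, so the number of affected findings cannot be estimated.

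**The case against.** The strongest defence is that little is lost. The general reporting rules give counts by arm, the ITT set stands in for the safety set, clinically important findings become adverse events, the protocol's only safety endpoint is AE incidence, and no formal inference rests on secondary endpoints. Since SAP 4.2 and 5.3 agree with the protocol, SAP 9.2 may also be a drafting slip and not a decision.

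Most of this stands, and it limits the size of the point. It does not remove it. The general rules promise frequencies of observed levels but define no slit lamp variable, and the section 9 rule would place the result under efficacy. A drafting slip in the operative analysis section still directs the programmer to the wrong model and the wrong heading.

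Stronger readings are tempting, and the documents do not support them:

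- A reader might infer that slit lamp data would have no summary at all, or would never enter the safety analysis. SAP sections 8 and 9 and the AE definition in Protocol 9.6.1.1 show otherwise.
- A reader might infer that the PP set hides ocular harm, because SAP 7.2.2 counts withdrawals for adverse events among early terminations. In the sponsor's previous trial, 4 subjects on OmegaD and 1 on placebo withdrew for that reason, so a PP display could be uneven. But SAP 9.2 also requires the ITT analysis, which keeps those subjects, and SAP 7.2.3 makes PP supportive.
- A reader might infer that safety data were moved deliberately. Nothing in the documents shows intent, and the agreement of SAP 4.2 and 5.3 with the protocol points the other way.

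**Conclusion.** SAP 9.2 is wrong as written, at low severity. It contradicts the protocol's classification, the protocol's form of safety reporting, and the SAP's own list of secondary endpoints, and it applies a linear model to findings for which no numeric variable exists. The loss is a valid summary, labelled as safety, of Day 42 and Day 84 slit lamp findings that do not qualify as adverse events. Neither primary endpoint changes, and AE incidence is reported in full.

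This rests on two assumptions: that the eCRF holds findings by structure and eye, as the protocol's description suggests, and that it holds no severity grade, since none is defined. The eCRF itself is not among the documents.

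**What to change.** Delete slit lamp examinations from SAP 9.2. In SAP 10.7, replace N/A with a descriptive table on the safety population, by arm and for each structure, that gives:

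- the number and percent of subjects with any abnormality in either eye at Baseline, Day 42 and Day 84;
- the number and percent of subjects with an abnormality that was absent at Baseline and present at Day 42 or Day 84.

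Use the subject as the counting unit and the number examined at the visit as the denominator. Add a row for worsening only if the eCRF grades severity, because the protocol defines no grade. If an efficacy role for slit lamp is really intended, it needs a defined variable, a categorical method and an entry in the protocol and in SAP 4.2, in addition to the safety table.

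The cost is one deletion, a short paragraph and one table. No new data are needed, and sample size, primary analysis and multiplicity are untouched.
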